AEs will be summarized by the Device sponsor CRA. Device sponsor management and the site PI will regularly convene to monitor and review AE reports. All AEs will be evaluated on an individual basis to determine whether the occurrence may be related to device use. Should a serious adverse event (SAE) occur that is deemed to be likely related to device use, the potential for the universality will be assessed within 48 hours. If evidence suggests that treatments with the device could create a safety concern for participants, the study Device sponsor will be pause or stop the study early, as appropriate.

It should be noted that the above scenario is considered to be highly unlikely. The device has been designated as NSR by the FDA, and there were no reports of significant or unexpected AEs

that were potentially related to device in either the PD single-site RCT or the episodic migraine RCT.

Participant Discontinuation/Withdrawal from the Study:

Withdrawal Criteria

Study participants must be withdrawn from the clinical trial if any of the following events occur:

- the participant is significantly and willfully non-adherent to the requirements of the protocol (principal investigator & Device Sponsor decision),
- the participant develops an illness (adverse event) that would interfere with his/her continued participation,
- the participant withdraws his/her consent,
- the principal investigator feels that it is the participant's best interest to be withdrawn,
- SNS discontinues the study or has achieved the targeted enrollment

If the study participant is discontinued from the participation in the study for any reason, the principal investigator must make every effort to perform all evaluations for the final visit, collect the device from the participant (if it is still within their possession) and document the reasons for discontinuation. If the participant withdraws from the study due to an adverse event that is potentially related to use of the device, the coordinator should continue to follow up with the participant at regular intervals, and at least every two weeks until the AE resolves or until the participant withdraws consent for the follow-up procedure. Reasons for study withdrawal should be documented on the subject disposition form.

Lost to Follow-up

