Any unanticipated problems, serious and unexpected adverse events, deviations or protocol changes will be documented and promptly reported by the principal investigator or designated member of the research team to the IRB and Device sponsor or appropriate government agency if appropriate.

AEs, ADEs, SAEs, SADEs and UADEs will be defined per ISO14155:2011 and/or 21 CFR Part 812, as described below.

Adverse Event (AE):

An AE is any untoward medical occurrence, unintended disease or injury, or untoward clinical signs (including abnormal laboratory findings) in subjects, users or other persons, whether or not related to the investigational medical device. This definition includes events related to the investigational medical device and the procedures involved. For users and other persons, this definition is restricted to events related to the investigational device. AEs will be collected starting from the time the subject signs informed consent until the follow-up period is completed.

Serious Adverse Event (SAE):

A Serious AE (SAE) is an AE that has

- a) Led to death,
- b) Led to serious deterioration in the health of the subject, that either resulted in
 - 1) A life-threatening illness or injury, or
 - 2) A permanent impairment of a body structure or a body function, or
 - 3) In-patient or prolonged hospitalization, or
 - 4) Medical or surgical intervention to prevent life-threatening illness or injury or permanent impairment to a body structure or a body function,
- c) Led to fetal distress, fetal death or a congenital abnormality or birth defect

Adverse Device Effect (ADE):

An Adverse Device Effect (ADE) is an AE related to the use of an investigational medical device.

This definition includes AEs resulting from insufficient or inadequate instructions for use, deployment, implantation, installation, or operation, or any malfunction of the investigational medical device.

This definition includes any event resulting from use error or from intentional misuse of the investigational medical device.

Traditional, diagnostic CVS has been used for roughly a century, and there are no reports in literature of significant adverse events.

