
- **Causality and Severity assessment**
 - The investigator will promptly review documented AEs to determine 1) if there is a reasonable possibility that the adverse event was caused by the investigational device or other study treatments and 2) if the adverse event meets the criteria for “*serious*.”
 - If the investigator’s final determination of causality is “of possible or probable relationship to the investigational device or other study treatments,” the adverse event will be classified as “*associated with the use of the investigational device or other study treatments*” for reporting purposes and escalated to the Device sponsor for further evaluation. If the investigator’s final determination of causality is “*not related* to the investigational device or other study treatments,” this determination and the rationale for the determination will be documented.

- **Investigator Reporting AEs to the Sponsor and responsible IRB Reporting to the Sponsor:**

- Adverse events will be submitted to the Sponsor.
- All serious and/or unanticipated adverse events will be submitted to the sponsor as soon as possible, but in no event later than 10 days after the investigator first learns of the event.
- All serious and/or unanticipated/unexpected adverse events that involves a death must be reported within **24 hours** of discovery.

Reporting to the IRB:

- Investigators are additionally required to submit to their IRB a report of Unanticipated Adverse Device Effect (UADE) as soon as possible, but in no event later than 10 working days after the investigator first learns of the event (21 CFR 812.150(a)(1)). However, if the UADE involves a death, it must be reported within 24 hours of discovery.

UADEs will require unblinding but written permission must first be obtained by the study sponsor.

- **Sponsor Reporting AEs to the FDA or Competent Authority:**

Upon receiving a report of a serious or unanticipated adverse device effect (or unexpected serious adverse device event), the Sponsor will immediately conduct an evaluation of the event/effect and report the results as follows:

- The Sponsor will report the results of an UADE to FDA, reviewing IRB, and participating investigators within 10 working days after the sponsor first receives notice of the effect (21 CFR 812.46[b], 21 CFR 812.150[b][1]). Thereafter, the sponsor shall submit such additional reports concerning the effect, as needed.

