- If the Sponsor determines that an UADE presents an unreasonable risk to participants, the Sponsor shall terminate all investigations or parts of investigations presenting that risk as soon as possible, no later than 5

working days after the sponsor first received notice of the effect.

Device Deficiencies

A device deficiency is an inadequacy of a medical device related to its identity, quality, durability, reliability, safety, or performance, such as malfunction, misuse or use error and inadequate labeling.

All device deficiencies will be documented, and the device should be returned to the device manufacturer for analysis, if possible. Instructions for returning the investigational device will be provided. Device deficiencies should also be documented in the study participant's source documents in the study binder. Device deficiencies are NOT to be reported as AEs. However, if there is an AE that results from a device deficiency, that specific event would be recorded on the appropriate CRF.

References

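### A non-fatal SAE, even a life-threatening one, need not reach the sponsor for 10 days, although the study-wide pause is the sponsor's decision and the 48-hour assessment has no defined start

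*Combined protocol and SAP*

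**What the plan says.** All references are to the combined protocol and SAP.

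- **Site to sponsor** (Procedures for AEs, investigator reporting to the sponsor): serious and/or unanticipated events must be "submitted to the sponsor as soon as possible, but in no event later than 10 days after the investigator first learns of the event". The exception is fatal events: "All serious and/or unanticipated/unexpected adverse events that involves a death must be reported within" 24 hours of discovery.
- **Joint review** (Discontinuation of Study Intervention): "Device sponsor management and the site PI will regularly convene to monitor and review AE reports". No meeting frequency is given.
- **Assessment** (same section): if an SAE is deemed likely related to the device, "the potential for the universality will be assessed within 48 hours". The text does not say when the 48 hours begin.
- **Pause or stop** (same section): if a safety concern is suggested, "the study Device sponsor will be pause or stop the study early, as appropriate". No deadline is attached.
- **Sponsor evaluation** (Sponsor Reporting AEs to the FDA or Competent Authority): once it has a report of a serious or unanticipated device effect, "the Sponsor will immediately conduct an evaluation of the event/effect".
- **UADE termination** (same section): for a UADE posing unreasonable risk, termination is due no later than 5 "working days after the sponsor first received notice of the effect".
- **General duty** (Reporting of Unanticipated Problems, Adverse Events or Deviations): unanticipated problems and serious, unexpected events are to be "promptly reported by the principal investigator or designated member of the research team to the IRB and Device sponsor". No number of hours or days is given.
- **Causality** (Causality and Severity assessment): the final determination is the investigator's, after prompt review.
- **Oversight** (Data and Safety Monitoring): there is no DSMB.

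**The concern.** The SAE definition covers life-threatening events, permanent impairment and hospitalisation. If the participant survives, any of these falls under the 10-day limit and not the 24-hour one. The only party that can pause the study as a whole is the sponsor, and no independent board might hear of the event by another route. Each sponsor-side time limit starts when the sponsor is told, so none of them shortens the 10 days.

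The 48-hour assessment is the protocol's main rapid safeguard for a likely device-related SAE. With no stated start, it cannot be audited, and its relation to the 10-day limit depends on how the reader takes it. What is at stake is how long other participants might go on treating twice daily before a study-wide decision. The estimates, error rates and endpoints are not affected.

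**Working it through.** The protocol gives no combined figure to reproduce. The check adds its stated limits, counting from the day the investigator learns of the event (day 0).

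**Inputs.** Site to sponsor, non-fatal SAE: 10 days. Site to sponsor, fatal event: 24 hours = 1 day. Assessment: 48 hours = 2 days. UADE termination: 5 working days from sponsor notice, which is 7 calendar days after a weekday notice, 6 after a Saturday and 5 after a Sunday (holidays ignored). Treatment: 2 sessions per day for 84 days = 168 sessions (Treatment period; Description of Study Intervention).

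**Step 1: does any other provision set a shorter limit for a non-fatal SAE?**
- The sponsor's immediate evaluation starts on receipt of a report.
- The UADE termination limit starts at sponsor notice.
- The prompt-reporting duty and the investigator's prompt causality review have no number. Nor does the escalation of possibly or probably related events to the sponsor.
- The request to the sponsor for permission to unblind (Randomization, Blinding and Unblinding) concerns a SADE or UADE that also requires treatment to stop, and has no time limit.

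None does. The outer limit on sponsor notice is day 10.

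**Step 2: the 48 hours under each possible start.**
- *From sponsor receipt, event already judged likely related:* 10 + 2 = day 12. For a fatal event: 1 + 2 = day 3.
- *From the investigator's relatedness call:* with a call on day 0, the assessment is due at 0 + 2 = day 2, while the sponsor need not be told until day 10. The assessment would fall due up to 8 days before the party that decides on a pause had to know.

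**Step 3: sensitivity to the word days.** The sponsor limit says days; the IRB limit just below it says working days. If working days were meant, 10 working days are 12 to 14 calendar days, and the assessment in the first case falls at day 14 to 16. Day 12 takes the shorter meaning.

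**Step 4: UADE termination.** 10 + (5 to 7) = day 15 to 17.

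**Step 5: exposure while the sponsor need not know.** 2 × 10 = 20 sessions for each participant still treating, of 168. By day 12 it is 2 × 12 = 24. Allocation is 1:1, so about half of those participants would be on the unpowered condition.

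**Step 6: with a 24-hour limit for all SAEs, and 48 hours from the later of sponsor receipt and the likely-related determination.** If the relatedness call accompanies the report: 1 + 2 = day 3, which is 12 − 3 = 9 days sooner than in the first case of Step 2. UADE termination: 1 + (5 to 7) = day 6 to 8.

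**The case against.** The best reply is that the 10 days are a backstop and not a schedule. The operative duty is to report as soon as possible, and a site that held a likely-related SAE until the last day would breach it. The investigator must review causality promptly. A UADE calls for unblinding, which needs the sponsor's written permission, so the sponsor must be contacted in any case. The site's principal investigator oversees every participant and can withdraw any of them in their own interest without waiting for the sponsor. The trial has one site and up to 20 participants, the device is designated non-significant risk, and the earlier trials are reported to have had no serious device-related events. All of this stands. It makes a full 10-day delay unlikely and keeps the severity low. It does not put a number on sponsor notice, and withdrawing individuals is not the same as a study-wide pause.

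A second reply is that day 12 depends on a clock the protocol never defines. That also stands, which is why both starts are shown above.

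A reader might infer more than the text supports:
- *That the study would be paused by day 12.* The 48 hours cover only the assessment. The pause has no deadline and could come later.
- *That the 10-day and 48-hour limits contradict each other.* They are out of step only if the 48 hours run from the site's relatedness call. From sponsor receipt they are consistent.
- *That the plan breaks a rule.* Nothing in the documents shows this. The protocol itself cites a regulation that allows 10 working days for UADE reports to the IRB. The 24-hour limit proposed here is a design improvement modelled on the protocol's own rule for deaths.

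**Conclusion.** The concern holds as a low-severity safety point. The protocol permits up to 10 days before the sponsor, who alone decides on a study-wide pause, need be told of a non-fatal SAE, and no other provision sets a shorter numeric limit. This rests directly on the stated text.

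The day-12 figure is narrower. It applies to an SAE judged likely device-related and dates the assessment, not the pause. It assumes a report on the last permitted day, calendar days, a relatedness call already made, and a 48-hour clock that starts at sponsor receipt. A later relatedness call would push it further out. It is a permitted worst case and should not be read as a forecast of events or of site behaviour.

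**What to change.** Two wording changes:

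1. In the investigator-to-sponsor reporting rule, require every SAE, whatever its causality status, to reach the sponsor within 24 hours of investigator awareness, as is already required for deaths. The 10-day limit can stay for unanticipated events that are not serious.
2. In Discontinuation of Study Intervention, state that the 48 hours run from the later of sponsor receipt and the determination that the SAE is likely device-related. Leave the final causality determination with the investigator, as the Causality and Severity assessment text has it. Giving it to a joint sponsor and investigator review would create a new inconsistency.

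The first change caps sponsor notice at 1 day instead of 10. The second gives the assessment a start that can be checked. If the relatedness call comes after the report, the assessment is due 48 hours after the call, so the existing duty of prompt causality review still matters.

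The cost is the two edits, a reminder to the site, and slightly faster SAE paperwork at one site with up to 20 participants, including for SAEs later judged unrelated. Sample size, endpoints and analysis do not change.
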